Data will be summarized using descriptive statistics (number of subjects, mean, median, standard deviation, minimum, and maximum) for continuous variables and using frequency and percentages for discrete variables.

The primary analysis will compare the distribution of the PFS between the two treatment arms by using the stratified Log-rank test, in which the stratification factors are IMDC risk category (favorable; intermediate; poor) and prior therapy (two prior VEGF TKIs; a prior checkpoint inhibitor [PD-1 or PD1-L inhibitor] plus a prior VEGFR TKI; a prior VEGFR TKI plus any other systemic agent). PFS will be based on the CT or MRI scan assessed by the IRR. PFS graphs will be presented by treatment arm.

The first secondary analysis will compare OS between the 2 treatment arms by using the stratified Log-rank test, the stratification factors included in the primary analysis, and two-sided 0.8% significance level (utilizing a Lan-DeMets alpha spending function with an O'Brien-Fleming boundary). An interim OS analysis will be done at the time of the final PFS analysis. It is expected that 149 OS events would have occurred at the time of final PFS analysis.

An interim analysis will be performed after 128 PFS events have been observed. The interim analysis will look into the study's futility using PFS as the efficacy evaluation endpoint. This will utilize a Lan-DeMets error spending-type function with an O'Brien-Fleming stopping boundary with an estimated two-sided beta (Type II error) of 1.2 % spent during this interim look. The interim analysis will be performed by an independent statistician. The independent statistician will evaluate and interpret the results of the interim analysis and will provide corresponding recommendation whether to stop the study for futility or for the study to continue until end of study condition has been met.

Two populations will be defined for the efficacy analysis: Intent-to-treat (ITT; defined as all subjects who were randomized into the study) and per protocol (PP; defined as all subjects in the ITT population who did not have major protocol deviations, have received at least two cycles (8 weeks) of protocol treatment, and met all eligibility criteria). Primary efficacy analysis will be based on ITT where subjects will be analyzed as randomized.

The safety population (SAF) will include all subjects who received at least one dose of either study drug. Subjects will be analyzed as treated.

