11.1 Criteria for Treatment Discontinuation (Stopping Rules)

Subjects will be discontinued from further treatment with study drug in the event of any of the following:

1. Death
2. Unacceptable toxicity considered by the investigator to require removal of the subject from study treatment.

Note: Adverse events resulting in a subject's permanent discontinuation from the study treatment, regardless of seriousness or relationship to study drug, MUST be promptly reported to the sponsor/designee. Subjects removed from treatment for intolerable toxicity should still be followed with regular tumor assessments (see Section 7.2.4) until disease progression or start of new treatment, and for survival thereafter.

3. Documented progressive disease according to RECIST Version 1.1 at any time during the study.
4. Subjects with radiological evidence of progressive disease per investigator/local radiology assessment should continue treatment until progressive disease is verified by an independent radiologist. Images should be submitted for independent review as soon as possible (see Imaging Manual for specific instructions). Verification of progressive disease is not required in the following circumstance:
 - Significant clinical deterioration that is indicative of progressive disease.
5. Subjects who have documented disease progression will be discontinued from study drug treatment and will continue to be followed up for survival.
6. Clinical progression (eg, symptomatic deterioration) not meeting the RECIST Version 1.1 criteria for radiological evidence of progressive disease but considered by the investigator to require removal of the subject from study. This includes subjects with significant clinical deterioration that is indicative of progressive disease. All related signs and symptoms of clinical progression must be captured in AE eCRF page, the term "progressive disease" should not be recorded as an adverse event or captured on the eCRF page.
7. Treatment interruption for > 4 weeks (ie, total duration of interruption, including the 1 week/cycle break in dosing of tivozanib), unless there is clear benefit from treatment, in which case the investigator must contact the medical monitor to review the subject's condition in order to resume treatment.
8. Requirement for a significant surgical procedure.

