14.3.1 Study Populations

Three populations will be used in the analyses of the data:

1. The intent-to-treat (ITT) population will consist of all randomized subjects; this population will be used for efficacy analysis, including primary endpoint (progression-free survival). Subjects will be analyzed as randomized.

2. The per protocol (PP) population is defined as all randomized subjects who received at least two cycles (8 weeks) of protocol treatment (unless discontinued due to death or disease progression), have no major protocol deviations that will confound the effects of treatment, and meet all eligibility criteria. Major protocol deviations include but are not limited to failure to satisfy eligibility criteria and taking prohibited medications during the treatment phase of the study. Subjects will be analyzed as treated.
3. The safety population (SAF) will include all subjects who received at least one dose of either study drug. Subjects will be analyzed as treated.

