14.3.4 Efficacy

The primary efficacy endpoint (PFS) and secondary efficacy endpoints (OS, ORR, and DoR) analyses will be carried out using the ITT population. The primary efficacy endpoint of PFS also will be analyzed using the PP population.

Analysis of the Primary Endpoint

The primary analysis is to compare the PFS of subjects dosed with tivozanib with those subjects dosed with sorafenib. The null hypothesis is that the median tivozanib PFS is equal to that of sorafenib and the alternative hypothesis is that the two PFS medians are not equal. The IRR will be the primary data source for the PFS analysis.

The primary analysis will be carried out by using a stratified Log-Rank test, in which the stratification factors are IMDC risk category (favorable; intermediate; poor) and prior therapy (two prior VEGFR TKIs; a prior checkpoint inhibitor [PD-1 or PD1 L inhibitor] plus a prior VEGFR TKI; a prior VEGFR TKI plus any other systemic agent), and using a two-sided 5% significance level. The distribution of the PFS will be estimated using the Kaplan-Meier method. The median event time and 2-sided 95% confidence interval for the median will be also provided.

Interim Analysis

An interim analysis will be performed after 128 PFS events have been observed. The interim analysis will look into the study's futility using PFS as the efficacy evaluation endpoint. This will utilize a Lan-DeMets error spending-type function with an O'Brien-Fleming stopping boundary with an estimated two-sided beta (Type II error) of 1.2 % spent during this interim look.

The interim analysis will be performed by an independent statistician. The independent statistician will evaluate and interpret the results of the interim analysis and will provide corresponding recommendation whether to stop the study for futility or for the study to continue until end of study condition has been met.

Final analysis performed on PFS will be based on 255 events. This could be performed ≥ 6 months after the last subject is accrued. PFS interim and final analyses will be carried out by using a stratified Log-Rank test with IMDC risk category and prior therapy as stratification factors.

Handling of Missing Data

For the purpose of PFS analyses, the following steps will be considered in case of missing data:

- a) Subjects with missing imaging at baseline will be considered non-evaluable for PFS estimation and will be excluded from the PFS analyses

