4.3 Study Subjects

4.3.1 Disposition of Subjects

A clear accounting of the disposition of all subjects who enter the study will be provided, from screening to end of study participation. Summaries of subject disposition presented by treatment arm and overall will be provided as follows:

- Number and percentage of subjects randomized
- Number and percentage of subjects randomized by region
- Number and percentage of subjects treated (i.e. received at least one dose of study drug treatment)
- Number of subjects in the analysis populations
- Number and percentage of subjects who withdrew early from the study (including reasons for early withdrawal)
- Number and percentage of subjects who withdrew early from treatment (including reasons for early withdrawal)

By-subject listings of randomization details, visit dates, and withdrawal details (including reason for discontinuation and duration of treatment prior to discontinuation) will also be provided.

4.3.2 **Protocol Deviations**

Major protocol deviations are defined as those deviations from the protocol likely to have an impact on the perceived efficacy and/or safety of study treatments. The impact of major protocol deviations on the efficacy and/or safety results will be investigated by assessing the robustness of the study results and conclusions to the choice of analysis population (see Section 4.4 for descriptions of analysis populations), both including and excluding data potentially affected by major protocol deviations.

A subject will be classified as having a protocol deviation if one incurs an event belonging to any one of the following categories: 1) violation of the inclusion/exclusion criteria; 2) taking prohibited medications or treatments; 3) treatment misallocation; 4) violation of discontinuation criteria; 5) error in procedure and tests; and 6) missed visits (including procedures and tests).

Major protocol deviations and any action to be taken regarding the exclusion of subjects are defined in the study protocol deviation specifications. The final determination of major protocol deviations and the exclusion of subjects from any of the analysis populations will be made prior to database lock.

A summary of the number and percentage of subjects with a major protocol deviation by treatment arm as well as by type of deviation will be provided. Also, a by-subject listing of major protocol deviations will be provided.

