4.4 Analysis Populations

- The intent-to-treat (ITT) population will consist of all randomized subjects; this population will be used for efficacy analysis, including primary endpoints. Subjects will be analyzed as randomized.
- The per-protocol (PP) population is defined as all randomized subjects who received at least two cycles (8 weeks) of protocol treatment, had no major protocol deviations that will confound the effects of treatment, and met all eligibility criteria. The PP population will be used as a sensitivity analysis for the assessment of the primary efficacy endpoint, and subjects will be analyzed as treated.
- The safety (SAF) population will include all subjects who received at least one dose of either study drug. Subjects will be analyzed as treated.

The efficacy summaries and analyses will be based on the ITT population. In the event that a subject is allocated the incorrect study treatment as per the study randomization list, subjects will be summarized and analyzed 'as randomized' (i.e. by randomized treatment arm). In the event that a subject is stratified incorrectly, 'randomized stratum' will be used rather than 'actual stratum'.

The safety summaries and analyses will be based on the SAF population. In the event that a subject is allocated the incorrect study treatment as per the study randomization list, subjects will be summarized and analyzed 'as treated' (i.e. by allocated treatment arm).

A by-subject listing of analysis population details will be provided. This listing will be presented by treatment arm and will include: center, subject identifier, inclusion/exclusion flag for each population, and reason for exclusion from each population.

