4.7.2 Primary Efficacy Variable – PFS

Primary Analysis on PFS

The primary variable for the assessment of efficacy is PFS, as defined in Section 3.2.1 of this SAP.

PFS based on IRR will be summarized for the ITT population using the Kaplan-Meier method. These summaries will include 1- and 2-year survival probabilities along with corresponding 95% CIs. Graphical displays (i.e. K-M plots), where appropriate, will also be produced.

Median event times and corresponding two-sided 95% CIs for the medians will be provided for PFS. A stratified log-rank test (one-sided, α =0.025) as well as hazard ratios and corresponding 95% CIs from a stratified Cox proportional hazard model, both adjusting for IMDC risk category and prior therapy, will be used to compare PFS between the two treatment arms.

When determining PFS, the recorded date of progression (defined as first time at which progression can be declared) will be used. For progression due to the presence of a new lesion, the date of progression is the first date that the new lesion was observed. If multiple assessments based on the sum of target lesion measurements are done at different times, the date of progression is the date of the last observation or radiological assessment of target lesions that shows a predefined increase in the sum of the target lesion measurements.

The robustness of the study results to the choice of baseline covariates will be investigated as described in Section 4.7.1.2. In addition, the homogeneity of the treatment effect for important subgroups will be investigated as described in Section 4.7.1.6.

A by-subject listing of the primary efficacy data will be provided.

Sensitivity Analyses on PFS

Sensitivity Analysis #1 will be done using the investigator assessment of response, adding in as events any clinical PDs specified by the investigator. A clinical PD is defined to be treatment failure not meeting the criteria for progressive disease but considered by the investigator to require removal of the subject from the study. This analysis will be conducted using the ITT and PP populations.

Sensitivity Analysis #2 will consider the initiation of new anti-tumor treatment to be an event. In this analysis, any death or PD will also be events, even those that occur after two or more missed tumor assessments. This analysis will be conducted using only the ITT population.

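### SAP 4.4 and the protocol synopsis omit the per-protocol exemption for early death or progression given in Protocol 14.3.1, so some subjects leave the PP set because of the PFS event itself

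*SAP*

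**What the plan says.** Three places define the PP set, and they do not agree.

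- SAP 4.4: "all randomized subjects who received at least two cycles (8 weeks) of protocol treatment, had no major protocol deviations". Subjects must also meet all eligibility criteria. There is no exemption.
- Protocol synopsis, statistical methods: subjects must "have received at least two cycles (8 weeks) of protocol treatment, and met all eligibility criteria". Again there is no exemption.
- Protocol 14.3.1: the same two-cycle minimum, but it does not apply to subjects who stopped early for one of two reasons: "unless discontinued due to death or disease progression".

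SAP 4.10, which records changes to the planned analysis, does not mention the difference.

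The PP set is used for PFS. Protocol 14.3.4 states: "The primary efficacy endpoint of PFS also will be analyzed using the PP population". SAP 4.4 calls PP a sensitivity analysis for the primary endpoint. For Sensitivity Analysis #1, SAP 4.7.2 states: "This analysis will be conducted using the ITT and PP populations". SAP 4.3.2 uses the populations to gauge the impact of major deviations, by "assessing the robustness of the study results and conclusions to the choice of analysis population".

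**The concern.** A PFS event is radiological progression or death from any cause (Protocol 14.3.4, SAP 3.2.1). Under the SAP wording, a subject who dies in week 5 has not had two cycles and leaves the PP set. The reason for leaving is the outcome being analysed, and the exemption in Protocol 14.3.1 prevents exactly this.

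Two things are at stake. First, a programmer working from the SAP would build a different PP set from the one in the body of the protocol. Second, a PP result that differs from ITT would mix the effect of protocol deviations, which SAP 4.3.2 wants to isolate, with the removal of early failures. How far the PP hazard ratio moves depends on how many early failures are removed from each arm, and no one can know that split when the rule is written.

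**Working it through.** **The plan's own figure.** Protocol 14.2 and SAP 4.9 give 255 PFS events for 90% power with medians of 4 and 6 months, so HR = 4/6 = 0.667. Schoenfeld's formula gives 4 × (1.960 + 1.282)² / (ln 0.667)² = 256 events, and 255 events give 89.9% power. The planning figure reproduces. Neither document gives a size for the PP set.

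**How many subjects could be affected.** Inputs: 161 per arm; PFS medians of 4 months (sorafenib) and 6 months (tivozanib); OS medians of 12 and 16 months (Protocol 14.2, SAP 4.9). Exponential times are assumed. The expected number of events by time t in one arm is 161 × (1 − 0.5^(t/median)).

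PFS and OS run from randomization, but treatment may start up to 14 days later (Protocol 5.1, SAP 3.1). Eight weeks of treatment can therefore end between 56 days (56 × 12/365.25 = 1.84 months) and 70 days (2.30 months) after randomization.

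| Events within | Sorafenib | Tivozanib | Total of 322 |
|---|---|---|---|
| 56 days, deaths | 16.2 | 12.3 | 28.6 |
| 56 days, PFS events | 44.0 | 30.8 | 74.8 |
| 70 days, PFS events | 52.9 | 37.6 | 90.5 |

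The PFS rows overstate the number removed. The first scheduled scan is at week 8 after Cycle 1 Day 1 (SAP 3.2.1), and subjects with local progression normally stay on treatment until it is independently verified (SAP 3.1). Most subjects whose progression is found at that scan will therefore have had two cycles. Those removed should mainly be early deaths and progression seen on early unscheduled scans. The death row may also be high, because entry requires a life expectancy of at least 3 months (Protocol 6.1).

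**Effect on the PP hazard ratio, proportional hazards.** Simulation: 161 per arm, exponential PFS with medians 4 and 6 months, uniform accrual over 15 months, cut at the 242nd event (the target in Protocol 5.3), unstratified Cox model, 1,500 replicates. Twenty events before week 8 are then removed. The number and the splits are assumptions.

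| 20 early events removed | HR before | HR after |
|---|---|---|
| At random from both arms pooled | 0.664 | 0.662 |
| 10 from each arm | 0.664 | 0.642 |
| All 20 from sorafenib | 0.665 | 0.760 |

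Pooled random removal takes events roughly in proportion to each arm's early event rate, so the ratio is nearly preserved. The other splits break that proportion and the ratio moves, in either direction.

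**Effect under non-proportional hazards.** Simulation with 15-month accrual plus 6 months of follow-up, 1,000 replicates, with every subject whose event falls before week 8 removed. This is an extreme case.

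- Benefit only in the first 8 weeks (HR 0.667, then 1): 0.90 in ITT, 1.00 in PP.
- No benefit until week 8 (HR 1, then 0.667): 0.77 in ITT, 0.67 in PP.

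**Precision.** Losing 20 of 242 events widens the confidence interval for the log HR by √(242/222) = 1.044, about 4%.

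**The case against.** The strongest reply is that little depends on this. The primary analysis is ITT in both documents, and among the numbered sensitivity analyses PP is named only for #1. If early events are lost roughly in proportion to each arm's early event rate, the PP hazard ratio hardly moves. All of that stands, and it limits the weight of the point. It does not reconcile the definitions. The statement that early PD counts as progression whatever the treatment duration (Protocol 9.1, SAP 3.1) concerns response assessment, not PP membership. The deviation specifications cited in SAP 4.3.2 are not among the documents reviewed, so they cannot be relied on to restore the exemption.

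A reader might infer more than the documents support:

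- *That the SAP made an undeclared change to the protocol.* The protocol disagrees with itself, and the SAP matches its synopsis. SAP section 1 names protocol Version 3.0 as its basis, and that version was not available for this review. An inherited inconsistency is the most that can be said.
- *That the eight-week rule treats the arms differently because tivozanib has a week off.* By the exposure formula in SAP 3.2.2, two full cycles last 49 days on tivozanib and 56 on sorafenib. But no passage applies that formula to PP membership. Protocol 7.2.1 and SAP 3.1 define a cycle as four weeks in both arms, and SAP 4.4 itself equates two cycles with eight weeks.
- *That the exemption is unusable because it does not say whether clinical progression counts.* Protocol 11.1 does list separately "Clinical progression (eg, symptomatic deterioration) not meeting the RECIST Version 1.1 criteria for radiological evidence of progressive disease", and Sensitivity Analysis #1 works by "adding in as events any clinical PDs specified by the investigator". This is detail left open, not an error, and the correction does not depend on it.
- *That 75 events is a ceiling, or that the PP hazard ratio is safe whenever hazards are proportional.* Neither holds. The count is about 90 if treatment starts 14 days after randomization, and uneven removal moves the ratio even under proportional hazards.

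**Conclusion.** The mismatch is real, and the SAP definition is wrong as written: it makes PP membership depend on the endpoint that the PP analysis measures. The consequence is confined to the PP analyses of PFS. The ITT primary analysis and the ITT sensitivity analyses do not change.

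The size is uncertain. The planning assumptions give about 29 early deaths; the larger PFS counts of about 75 to 90 probably lie well above the number that would be removed. For an assumed 20 removals under proportional hazards, the PP hazard ratio ranges from essentially unchanged to 0.64 or 0.76, depending on the split between arms. Under non-proportional hazards it can move either way. These figures rest on exponential times and assumed splits. They show that the PP estimate is sensitive to the rule; they do not forecast what will happen in this trial. The point should be corrected because the remedy is small and the protocol already contains it.

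**What to change.** Insert "unless discontinued due to death or disease progression" after the two-cycle requirement in SAP 4.4 and in the protocol synopsis, so that all three definitions agree with Protocol 14.3.1. If the omission is intended, record it in SAP 4.10 with a reason. Either should be done before database lock, when SAP 4.3.2 requires population exclusions to be final.

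The cost is one phrase in two places. The PP flag must then use the reason for discontinuation as well as treatment duration, and SAP 4.3.1 already lists both by subject. The correction reduces the mixing of early discontinuation with protocol deviations in the ITT–PP comparison but does not remove it, because subjects who stop before two cycles for toxicity or withdrawal still leave the PP set.

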4.5 Demographic and Other Baseline Characteristics

The following demographic and baseline characteristics will be summarized for subjects in the ITT population by treatment arm:

- Age at time of informed consent (in years, as a continuous variable)
- Age categorization (<65, >= 65 years)
- Gender (Male, Female)
- Race (White, Black/African American, Asian, American Indian/Alaska Native, Hawaiian Native/Other Pacific Islander, Unknown, Other, Decline to State)
- Ethnicity (Hispanic or Latino, Not Hispanic or Latino, Unknown, Decline to State)
- Geographic region [North America (NA), European Union (EU), Rest of World]
- Weight at screening (in kilograms)

- Height at screening (in centimeters)
- BMI at screening (in kg/m^2) calculated using weight and height at screening
- Baseline systolic blood pressure (<=140 mmHg, >140 mmHg)
- Baseline diastolic blood pressure (<=90 mmHg, >90 mmHg)
- IMDC risk category (Favorable, Intermediate, Poor)
- Prior therapy (Two Prior VEGFR TKIs, Prior Checkpoint Inhibitor Plus VEGFR TKI, Prior VEGFR TKI Plus Other Systemic Agent)
- Baseline Eastern Cooperative Oncology Group (ECOG) performance status (0, 1)
- Primary diagnosis:
 - Time from initial diagnosis to randomization (in months)
 - Time from most recent relapse or staging to randomization (in months)
 - Pathological diagnosis (Clear Cell, Clear Cell Component, Other)
 - Diagnosis confirmation method (Histology, Cytology, Other)
 - Stage at screening [Stage IV (metastatic), Local Recurrence]
 - Metastatic site location
 - Type of metastases (Multiple Metastases, Solitary Metastases, No Involvement, Unknown)
- Primary disease:
 - Number of metastatic sites per subject
 - Prior radiotherapy (Yes, No)
 - Prior chemotherapy setting (Neo-adjuvant, Adjuvant, Metastatic/Unresectable Therapy, Other, Unknown)
 - Prior nephrectomy (Complete Nephrectomy, Partial Nephrectomy, Other)

Since age is part of the inclusion criteria, age will be calculated as the number of complete years between a subject's birth date and the date of informed consent.

